5.5.8 Prohibited medication

Use of the treatments displayed in Table 5-1 is NOT allowed after the start of the washout period.

Live vaccines should not be given until 12 weeks after last study treatment administration.

Prohibited medication	Washout period (before randomization)
Etanercept*	4 weeks
Infliximab*	8 weeks
Adalimumab, golimumab, certolizumab*	10 weeks
Biological immunomodulating agents* except TNF inhibitors as described above	Never
Unstable dose of MTX or sulfasalazine (until Week 24)	4 weeks
Other DMARD (incl. apremilast, except MTX and – in case of axSpA - sulfasalazine)	4 weeks
Leflunomide	8 weeks
Leflunomide with cholestyramine washout	4 weeks
Unstable doses of NSAIDs (COX1 or COX2 inhibitors), low strength opioids, paracetamol/acetaminophen (until Week 24). After week 24, use PRN is allowed.	2 weeks
Analgesics, other than NSAIDs or paracetamol/acetaminophen or low strength opioids as described above	2 weeks
Systemic corticosteroids > 10 mg prednisone equivalent** (until Week 52)	2 weeks
Unstable dose of systemic corticosteroids \leq 10 mg prednisone equivalent (until Week 24)	2 weeks
Intra-articular injections (until Week 24)	4 weeks
Intramuscular or intravenous corticosteroid treatment	4 weeks
Any cell-depleting therapies including but not limited to anti-CD20 or investigational agents (e.g., CAMPATH, anti-CD4, anti-CD5, anti-CD3, anti-CD19)	Never
Any investigational treatment or participation in any interventional Trial	4 weeks or 5 half-lives (whichever is longer)

Table 5-1	Prohibited	medication

Prohibited medication	Washout period (before randomization)
Live vaccines (and until 12 weeks after last study treatment administration, see above)	6 weeks
Oral or topical retinoids	4 weeks
Photochemotherapy (e.g. PUVA)	4 weeks
Phototherapy (UVA or UVB)	2 weeks
Topical skin treatments (except in face, eyes, scalp and genital area during screening, only corticosteroids with mild to moderate potency)	2 weeks

Abbreviations: COX = cyclo-oxygenase, DMARD = disease modifying anti-rheumatic drug, MTX = methotrexate, NSAIDs = non-steroidal anti-inflammatory drugs, PRN = pro re nata (as needed); PUVA = psoralen and ultraviolet A; UVA = ultraviolet A; UVB = ultraviolet B: TNF = tumor necrosis factor. * These agents fall under the category of biologic immunomodulators and are prohibited medications. Administration of these agents requires study treatment discontinuation (see Section 5.6.2). ** See details about corticosteroid management in Section 5.5.7.

5.5.9 Emergency breaking of assigned treatment code

Emergency code breaks must only be undertaken when it is required to in order to treat the patient safely. Most often, study treatment discontinuation and knowledge of the possible treatment assignments are sufficient to treat a study patient who presents with an emergency condition. Emergency treatment code breaks are performed using the IRT. When the investigator contacts the system to break a treatment code for a patient, he/she must provide the requested patient identifying information and confirm the necessity to break the treatment code for the patient. The investigator will then receive details of the investigational drug treatment for the specified patient and a fax or email confirming this information. The system will automatically inform the Novartis monitor for the site and the Study Team that the code has been broken.

It is the investigator's responsibility to ensure that there is a dependable procedure in place to allow access to the IRT at any time in case of emergency. The investigator will provide:

- protocol number
- study drug name (if available)
- patient number

In addition, oral and written information to the patient must be provided on how to contact his/her backup in cases of emergency, or when he/she is unavailable, to ensure that unblinding can be performed at any time.

Study drug must be discontinued after emergency unblinding.

5.6 Study completion and discontinuation

5.6.1 Study completion and post-study treatment

A patient will be considered to have completed the study when the patient has completed the last visit planned in the protocol i.e. Visit 18/Week 52 (see Table 6-1).

Information on the patient's completion or discontinuation of the study and the reason for discontinuation of the study will be recorded on the appropriate Study Phase Completion

eCRF page. In any case, the investigator or site staff must contact the IRT as soon as possible to record the patient's study completion and/or discontinuation.

The investigator must provide follow-up medical care for all patients who are prematurely withdrawn from or complete the study or must refer them for appropriate ongoing care. This care may include initiating another treatment outside of the study as deemed appropriate by the investigator. Based on the individual risk/benefit profile of a patient, treatment may be any non-biologic DMARD. In case of a biologic treatment, a waiting period of 3 months before initiating the treatment is recommended.

nr-axSpA patients with objective signs of inflammation at Screening, evident by either MRI with sacroiliac joint inflammation (according to source documentation) and/or hsCRP > ULN (as defined by central lab) who successfully complete the 1 year trial duration and were benefiting from secukinumab may be given the opportunity to enter an extension study. If an extension study is agreed on, it will be described in a separate extension study protocol.

5.6.2 Discontinuation of study treatment

Discontinuation of study treatment for a patient occurs when study drug is stopped earlier than the protocol planned duration, and can be initiated by either the patient or the investigator.

Patients may voluntarily discontinue from the study for any reason at any time. They may be considered discontinued if they state an intention to withdraw, fail to return for visits, or become lost to follow-up for any other reason.

Study treatment must be discontinued if the Investigator determines that continuation of study treatment would result in a significant safety risk for a patient.

The following circumstances require study treatment discontinuation:

- Withdrawal of informed consent
- Emergence of the following AEs:
 - Any severe or SAE that is not compatible with administration of study medication, including AEs that require treatment with an unacceptable concomitant medication.
 - Onset of lymphoproliferative disease or any malignancy, except for treated basal cell carcinoma, treated actinic keratoses, treated in situ carcinoma of the cervix or non-invasive malignant colon polyps which are being or have been removed.
 - Life-threatening infection.
 - Severe hypersensitivity reaction or anaphylactic reaction.
- Any laboratory abnormalities that in the judgment of the investigator are clinically significant and are deemed to place the patient at a safety risk for continuation in the study (A general guidance on clinically notable laboratory values is provided in Appendix 1).
- Pregnancy.
- Use of any biologic immunomodulating agent except secukinumab.
- Any protocol deviation that results in a significant risk to the patient's safety.

In addition to these requirements for study treatment discontinuation, the investigator should discontinue study treatment for a given patient if on balance, he/she thinks that continuation would be detrimental to the patient's well-being. While PsA and axSpA are multifaceted diseases and the assessment of responder status should be based on the global clinical picture and not on a single efficacy parameter; not achieving an improvement (e.g. in the TJC or SJC

Novartis	Confidential	Page 4
Amended Clinical Trial Protocol Version 03	clean	Protocol No. CAIN457F330

of $\geq 20\%$ [PsA patients]) or BASDAI of $\geq 20\%$ or ≥ 1 unit (0-10 scale) (axSpA patients, Pavy et al 2005) at Week 36 may be considered as a guidance for considering a patient inadequate responder to secukinumab treatment.

For patients who discontinue study treatment, a Dosage Administration Record eCRF should be completed, giving the date and primary reason for stopping study treatment.

The investigator must also contact the IRT to register the patient's discontinuation from study treatment.

If study drug discontinuation occurs because the treatment code has been broken, please refer to Section 5.5.9.

Patients who prematurely discontinue during Treatment Period 1 (secukinumab/placebo treatment from Baseline through Week 24) should return for assessments associated with Week 24 visit (4 weeks after the last study treatment in Treatment Period 1). Patients who prematurely discontinue during Treatment Period 2 (secukinumab treatment from Week 24 through Week 52) should return and complete assessments associated with Week 52 visit (4 weeks after the last study treatment in Treatment Period 2, see Table 6-1). The final visit should be performed before any new treatment is initiated.

Patients who prematurely withdraw from the study will not be replaced.

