	This includes any placebos, any active controls, as well as approved drugs used outside of their indication/approved dosage or tested in a fixed combination.
	Study treatment generally does not include protocol-specified concomitant background therapies when these are standard treatments in that indication.
Medication number	A unique identifier on the label of each study drug package in studies that dispense medication using an interactive response technology (IRT) system.
Mis-randomization	A patient who is randomized to a treatment group, but did not receive any study treatment.
Period	The planned stage of the patient's participation in the study. Each period serves a purpose in the study as a whole.
Protocol	A written account of all the procedures to be followed in a trial, which describes all the administrative, documentation, analytical and clinical processes used in the trial.
Premature patient withdrawal	Point/time when the patient exits from the study prior to the planned completion of all study treatment administration and/or assessments; at this time all study treatment administration is discontinued and no further assessments are planned, unless the patient will be followed for progression and/or survival.
Randomization number	A unique identifier assigned to each randomized patient, corresponding to a specific treatment arm assignment.
Re-screening	A patient who qualified for all or most eligibility criteria but could not be randomized within the screening period can be considered for rescreening only once.
Rescue medication	Any new therapeutic intervention or a significant change to ongoing therapy made because a patient is experiencing either no benefit from participation in the trial or worsening/ exacerbation of their disease.
Responder	A patient with \ge 20% improvement from Baseline in both tender joint count (TJC) and swollen joint counts (SJC).

Study treatment discontinuation	Point/time when patient permanently stops taking study treatment for any reason; may or may not also be the point/time of premature patient withdrawal.
Patient number	A number assigned to each patient who enrolls into the study.
Variable	A measured value or assessed response that is determined in specific assessments and used in data analysis to evaluate the drug being tested in the study.

Amendment 3

Amendment rationale

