5.2 Treatment arms

Patients will be randomized to one of the following 2 treatment groups in a 1:1 ratio as depicted below:

- Group 1: secukinumab 150 mg/300 mg s.c.: secukinumab as 1 (1.0 mL PFS of 150 mg dose) s.c. or 2 (2 × 1.0 mL PFS of 150 mg dose, 300 mg) s.c. injections at Baseline, Weeks 1, 2, and 3, followed by administration every 4 weeks starting at Week 4.
 - PsA patients, who have been previously exposed to TNF blockers, and/or with concomitant moderate to severe plaque psoriasis receive 2 (two) 1.0 mL PFS of 150 mg dose (i.e. 300 mg) s.c..
 - Other PsA patients and axSpA patients receive 1 (one) 1.0 mL PFS of 150 mg dose s.c..
- Group 2: placebo s.c. followed by secukinumab 150 mg/300 mg s.c. at Baseline, Weeks 1, 2, and 3, followed by administration every 4 weeks starting at Week 4.2
 - PsA patients, who have been previously exposed to TNF blockers, and/or with concomitant moderate to severe plaque psoriasis receive placebo as 2 (two) 1.0 mL PFS s.c..
 - Other PsA patients and axSpA patients receive placebo as 1 (one) 1.0 mL PFS s.c..
 - At Week 24, all patients in Group 2 will switch to their pre-assigned secukinumab treatment

Patients will receive study treatment at Baseline, Weeks 1, 2, and 3, followed by treatment every 4 weeks through Week 52 (last dose given at Week 48). At Week 24, patients originally randomized to placebo will switch to receive secukinumab 150 mg (1 injection of secukinumab 1 mL/150 mg) or secukinumab 300 mg (2 injections of secukinumab 1 mL/150 mg) in open-label fashion without a loading regimen. Blinding to the original treatment assignment will be maintained until after the Week 52 database lock and analyses are completed (see Section 5.4). Patients will self-administer all secukinumab and placebo doses as described in Section 3.1 at the study site or at home at indicated study visits (see Table 6-1) through Week 52.

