5.6.5 Early study termination by the sponsor

The study can be terminated by Novartis at any time for any reason. This may include reasons related to the benefit risk assessment of participating in the study, practical reasons, or for regulatory or medical reasons (including slow enrolment). Should this be necessary, the patient must be seen as soon as possible and treated as a prematurely withdrawn patient. The investigator may be informed of additional procedures to be followed in order to ensure that adequate consideration is given to the protection of the patient's interests. The investigator will be responsible for informing the Institutional Review Board/Independent Ethics Committee (IRBs/IECs) of the early termination of the trial.

6 Visit schedule and assessments

Table 6-1 lists all of the assessments and indicates with an "x" when the visits are performed. During the period of the study from Screening to Week 52 (Treatment Periods 1 and 2), the assessments must be performed as indicated in Table 6-1.

Preferably, patients should be seen for all visits on the designated day, or within the recommended visit window to the original planned visit.

- For visits scheduled through Week 4, the study treatment should not be administered less than 7 days after the previous administration.
- For visits scheduled after Week 4, the study treatment should not be administered less than 14 days after the previous administration.

Note: Missed or rescheduled visits should not lead to automatic discontinuation of patients.

Recommended visit windows:

- ± 2 days for Baseline, Week 1, Week 2, Week 3 and Week 4, Week 24 and Week 52
- ± 2 days for all study drug home administrations
- ± 5 days for all other study visits

Patients who prematurely discontinue during a specific treatment period should return for the final visit within that treatment period (4 weeks after the last study treatment administration). At this final visit, all dispensed study product should be reconciled with the source documents including the AE and concomitant medications reconciled on the eCRF.

If patients refuse to return for these assessments or are unable to do so, every effort should be made to contact them or a knowledgeable informant by telephone to determine the reason. Documentation of attempts to contact the patient should be recorded in the source documentation.

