6.4.1.7 Magnetic resonance imaging

Disease severity and activity of PsA and axSpA can be evaluated by a variety of modalities, including magnetic resonance imaging (MRI). MRI has been frequently used to measure outcome of PsA because of its sensitivity in detecting changes in both bone and soft tissues (Yanaba et al 2015).

Effects on inflammation in the affected foot at Baseline will be assessed by MRI image analysis throughout the trial compared to pre-treatment including the following parameters (Feydy et al 2012):

- Bone marrow oedema in the insertion of the Achilles tendon in the upper part of the calcaneus and/or in the insertion of the plantar aponeurosis in the lower part of the calcaneus.
- Periarticular inflammation.
- Resolution of signs of active inflammation.
- Bone erosions.

MRI analysis will be performed at 3 time points i.e., during pre-treatment, Week 24, and Week 52. For patients who discontinue before or at Week 24, a MRI will be performed at the time of discontinuation. MRI machines should have field strength of 1.5 Tesla. The MRI protocol and required sequences will be described in the imaging acquisition manual.

Except for the local reading of the eligibility scan for trial participation, the readings and scoring will be performed centrally. Readers will be blinded to clinical information and to the sequence of the images.

Psoriatic arthritis magnetic resonance imaging scoring system

The PsAMRIS has been developed by the Outcome Measures in Rheumatology Clinical Trial (OMERACT, Ostergaard et al 2009, McQueen et al 2009) and was based on the OMERACT rheumatoid arthritis (RA) MRI scoring system (RAMRIS) (Ostergaard et al 2003, Haavardsholm et al 2005). The PsAMRIS has shown high inter- and intraobserver reliability (Bøyesen et al 2011) and it is thought that this scoring system will be useful in measuring outcomes in the treatment of PsA. It is composed of the following six subcomponents that are assessed by a defined grading scale: synovitis, tenosynovitis, periarticular inflammation, bone oedema, bone erosions, bone proliferation.

The PsAMRIS has been originally developed for the hands (Ostergaard et al 2009) but it has recently been applied in feet MRI image analysis (Yanaba et al 2015).

Feet MRI images will be assessed for the PsAMRIS subcomponents periarticular inflammation, bone oedema and bone erosion by their respective grading scale (Ostergaard et al 2003, Ostergaard et al 2009).

	•			

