9.4 Analysis of the primary variable

9.4.1 Variable

The primary endpoint variable is the percentage of patients with resolution of Achilles tendon enthesitis as assessed by the respective subcomponent of the LEI at 24 weeks. This resolution is referred to as 'response' below.

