9.4.4 Sensitivity analyses

A possible effect modification of patient characteristics will be explored by subgroup analyses for sex, age class, $TNF\alpha$ inhibitor status and disease severity at Baseline. The primary model

may also be recalculated with these factors included as well as with respective terms for a subgroup*treatment interaction. In case of a substantial number of missing values, alternative approaches to handle missing values (RMREM, MI) may be additionally calculated as sensitivity analyses.

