### 2.5.3 Handling of missing values/censoring/discontinuations

This study aims to estimate the magnitude of treatment effects that are obtainable under the respective treatments. The disease activity is expected to decrease in the course of treatment. If a patient drops out or discontinues the trial prematurely, the last observed value of that patient seems to be a proper estimate for the effect achieved in that patient.

For the primary endpoint, a patient with a missing assessment will be considered as a responder if he/she has met the response criterion already at the time of drop-out. Otherwise he/she will be considered as a non-responder.

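### Patients who stop treatment before their Week 20 dose have no planned assessment at calendar Week 24, and a resolution seen 4 to 20 weeks earlier counts as a Week 24 response

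*Protocol*

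**What the plan says.** The primary variable is the "percentage of patients with resolution of Achilles tendon enthesitis as assessed by the respective subcomponent of the LEI at 24 weeks" (Protocol 9.4.1). It is analysed on a full analysis set described as following intent-to-treat (Protocol 9.1, SAP 2.2).

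A patient who discontinues in Treatment Period 1 "should return for assessments associated with Week 24 visit (4 weeks after the last study treatment in Treatment Period 1" (Protocol 5.6.2, repeated in the asterisk footnote to Table 6-1). The introduction to Protocol section 6 says that such patients "should return for the final visit within that treatment period (4 weeks after the last study treatment administration". Table 6-1 places this visit in the Visit 11 column, which is shared by Week 24, treatment discontinuation and premature patient discontinuation.

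The protocol glossary treats stopping study treatment as a separate event that "may or may not also be the point/time of premature patient withdrawal". Protocol 5.6.3 rules out further assessments only once consent is withdrawn.

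The missing-data rule in the primary analysis reads: "a patient with a missing assessment will be considered as a responder if he/she has met the response criterion already at the time of drop-out" (SAP 2.5.3, same rule in Protocol 9.4.3); otherwise the patient is a non-responder. On sensitivity analyses, Protocol 9.4.4 says: "In case of a substantial number of missing values, alternative approaches to handle missing values (RMREM, MI) may be additionally calculated as sensitivity analyses".

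On imaging, Protocol 6.4.1.7 says: "For patients who discontinue before or at Week 24, a MRI will be performed at the time of discontinuation".

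**The concern.** The glossary allows a patient to stop the drug and stay in the study, but the visit schedule has no path for that patient. The only visit described is tied to the last dose, not to the calendar. The primary question is the state of the Achilles enthesis at Week 24 in everyone randomised. For early leavers the plan answers it with a value taken while drug effect may still be present, up to 20 weeks too soon. The stated reason for carrying that value forward is that disease activity should fall as treatment proceeds, which says little about a patient who is no longer treated.

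The Week 24 outcome of these patients is not collected, so no later analysis can recover it. The early visit also shares a column with the true Week 24 visit. The visible SAP text has no rule based on study day to keep the two apart in the primary or secondary analyses.

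**Working it through.** **1. The plan's own figure.** Protocol 9.8 gives 89 per arm for 45% vs 21%, two-sided 5%, 90% power. The normal-approximation formula gives 79 without and 87 with continuity correction, and exact Fisher power at 89 is 91.0%, so 89 is reproduced to within two patients. Recruiting 100 leaves an allowance of (100 - 89)/100 = 11% per arm for drop-outs and other violations. SAP section 3 attaches 2.5% to the same 89; that is a separate matter.

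**2. Timing.** Dosing: "Patients will receive study treatment at Baseline, Weeks 1, 2, and 3, followed by treatment every 4 weeks" (Protocol 5.2). Visit week = week of last dose + 4.

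| Last dose (week) | 0 | 1 | 2 | 3 | 4 | 8 | 12 | 16 | 20 |
|---|---|---|---|---|---|---|---|---|---|
| Visit (week) | 4 | 5 | 6 | 7 | 8 | 12 | 16 | 20 | 24 |

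Only a last dose at Week 20 leads to Week 24. All others are assessed 4 to 20 weeks early.

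**3. Route into the primary endpoint.** If the early visit is stored as Visit 11, its LEI is read as Week 24. If it is not, Week 24 is missing and the drop-out rule applies. Either way, a resolution seen then is a response.

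**4. Effect on the difference.** Let d be the proportion leaving early and r the proportion of leavers resolved at the early visit. Compared with counting leavers as non-responders, each arm's rate rises by d x r. With the same d in both arms, the difference changes by d x (r_sec - r_plc). Assumptions: d = 5-11%, r_sec = 20-30%, r_plc = 0-10%.
- Smallest: 0.05 x (0.20 - 0.10) = 0.5 points.
- Largest: 0.11 x (0.30 - 0) = 3.3 points.

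**5. What such a shift would do to the error rate.** Take true rates of 21% in both arms, n = 100 per arm, and an observed secukinumab rate of 21% + s. One-sided error = 1 - Φ[(1.96 x SE0 - s)/SE1], where SE0 uses the pooled and SE1 the separate variances. For s = 0.02: SE0 = √(2 x 0.22 x 0.78/100) = 0.0586, SE1 = √((0.21 x 0.79 + 0.23 x 0.77)/100) = 0.0586, and (0.1148 - 0.02)/0.0586 = 1.62, giving 5.3%.

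| Shift s (points) | 0 | 0.5 | 1 | 2 | 3 | 3.3 |
|---|---|---|---|---|---|---|
| One-sided error | 2.5% | 3.0% | 3.7% | 5.3% | 7.3% | 8.0% |

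**6. Direction.** Completers are set at 45% and 21%.
- 11% leave each arm, 30% of leavers resolved in both. Current rule: 0.89 x 45 + 0.11 x 30 = 43.4% vs 0.89 x 21 + 0.11 x 30 = 22.0%. Non-responder counting: 40.1% vs 18.7%. The difference is 21.4 points under both.
- 11% leave secukinumab and 22% placebo, 30% resolved in both. Current rule 20.4 points, non-responder counting 23.7. The current rule works against secukinumab.
- 22% and 11%, 30% resolved in both. Current rule 19.7 points, non-responder counting 16.4. The current rule favours secukinumab.
- 11% leave each arm, at the extremes of none or all resolved: secukinumab 40.1-51.1%, placebo 18.7-29.7%, difference 10.4-32.4 points.

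**7. Power after the change.** With 11% per arm counted as non-responders (40.1% vs 18.7%, n = 100), power is 91.9%.

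**The case against.** **A declared on-treatment aim.** Protocol 9.4.3 and SAP 2.5.3 say that the study seeks the effect obtainable on each treatment and regard the last value as a fair estimate of what that patient achieved. In the maintenance phase, 4 weeks after a dose is one dosing interval, the same gap as Week 20 to Week 24. This stands in part: it makes the choice of primary rule arguable. It does not explain why the outcome is left uncollected, and it sits uneasily with an intent-to-treat set and an endpoint named for Week 24.

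**A symmetric rule.** A reader might infer that the rule favours secukinumab. The documents do not support that: a resolved placebo leaver is also a responder. The inflated error rates require secukinumab leavers to resolve more often than placebo leavers even though the drug has no effect, and nothing in the documents supports such a gap.

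**Another reading of the visit rule.** Taken alone, the parenthesis in 5.6.2 could describe the scheduled visit, Week 20 plus 4. Section 6 refers to the last administration and to a final visit, and the column is shared with treatment discontinuation. The early reading is the better one, but the wording should be explicit.

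**Other inferences that go too far.** One is that early stoppers are never seen at Week 24; those last dosed at Week 20 are. Another is that the SAP has no sensitivity analysis for missing data; its table of contents shows a redacted heading directly after 2.5.3, so this cannot be known. A third is that heel pain, oedema or total LEI will take the early record as Week 24. That is possible, but no analysis-visit mapping is shown.

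**Conclusion.** The point holds for patients whose last Period 1 dose is before Week 20 and who have not withdrawn consent. As written, the plan schedules no calendar Week 24 assessment for them and lets a resolution seen at Weeks 4-20 count as the primary response.

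The size rests on assumed figures. With 5-11% leaving per arm and the unequal resolution shares in step 4, the difference moves 0.5-3.3 points relative to non-responder counting, and one-sided error under equal 21% rates would be about 3.0% to 8.0%. With equal numbers leaving and equal resolution, the difference does not move. Non-responder counting is itself only a reference; the true Week 24 outcomes are unknown under either rule. Nothing here shows that a trial with true rates of 45% and 21% would reach a wrong conclusion.

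Two lesser points follow. The MRI timing in 6.4.1.7 and in Table 6-1 can be read as the same visit but is worded differently. Period 2 has the same structure: a former placebo patient who stops after the Week 24 dose has a Week 52 visit at Week 28, although the results after the switch are descriptive only.

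The change should be made because it is cheap and the missing data cannot be recovered later.

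**What to change.** 1. **Protocol 5.6.2, section 6 and Table 6-1.** Keep the early-termination visit, under its own visit label. Ask patients who stop study treatment but have not withdrawn consent to attend the scheduled Week 24 visit as well, and likewise Week 52, for LEI, heel pain, the global assessments and SF-36, with no extra MRI. Record any new treatment started in between. Reconcile this with Protocol 3.1 and 5.5.6 and SAP 2.4.2, which discontinue patients from the study after prohibited rescue, and with the statement in 5.6.2 that the final visit precedes any new treatment.
2. **SAP visit assignment.** Assign early-termination assessments, including MRI, to analysis visits by study day, so that they are not analysed as observed Week 24 or Week 52 values.
3. **SAP 2.5.3.** Pre-specify an analysis that counts as non-responders all patients with no LEI in the Week 24 window and all who started prohibited rescue before it. Preferably make it primary, with the present carry-forward rule as sensitivity analysis. At minimum make it a mandatory sensitivity analysis.
4. **MRI.** Reconcile the timing in Protocol 6.4.1.7 with Table 6-1.

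**Cost.** Protocol and SAP wording; roughly 10 to 22 extra ordinary Week 24 visits if 5-11% of 200 patients stop early (0.05 x 200 = 10, 0.11 x 200 = 22), which is not a ceiling because the 11% is only an allowance; the Week 52 visits come on top. If non-responder counting becomes primary, stated response rates fall slightly, and power is about 92% in the 11% case.
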